C. Post prandial studies

Two postprandial studies are proposed for the subjects. The first is feeding a standard high fat meal followed by serial blood samples to assess the rise and fall of lipids and insulin in response to a high fat load. The fat load will include retinyl palmitate to monitor chylomicron turnover. The second uses "day-long" post prandial sampling collecting blood samples from fasting subjects in the morning and just before lunch (12-1 pm) and just before supper (4-5 pm). These samples would be analyzed for insulin, glucose and triglycerides, to provide an examination of lipoprotein levels over an entire day's duration.

1. Standard Fat Load Test: The protocol will be carried out as follows: Subjects will fast at least 12 hours prior to coming to the laboratory. A fasting blood sample will be obtained using the standard protocol for fasting blood tests. Subjects will then ingest the liquid formula fat load over a period of 10-15 minutes. Post fat load samples would be taken at 4 and 8 hours. Participants would not eat any food and could drink only water or diet, non-caloric, non-caffeine drinks during the 8 hours of the test. As described below, the liquid formula would also contain carbohydrate and this may allow for meaningful measures of glucose and insulin.

Rationale: Dietary fat and cholesterol are absorbed in the small intestine and incorporated into chylomicrons. After entry into the circulation, chylomicrons interact with lipoprotein lipase on the luminal surface of endothelial cells and the chylomicron triglyceride is hydrolyzed to fatty acids and glycerol. The product of the interaction between chylomicrons and lipoprotein lipase is the chylomicron remnant. These relatively cholesterol ester-enriched particles appear to be removed by one our more receptors in the liver. The process by which dietary triglyceride and cholesterol are transported and cleared from the circulation can be affected by chronic dietary patterns, particularly dietary fat and cholesterol intake. In our proposal we will use a standard fat-load to determine the effects of difference levels of dietary fat and carbohydrate on chylomicron and chylomicron remnant metabolism. The results of these studies will help us determine the optimal diet therapy for individuals with higher triglyceride and/or lower HDL cholesterol and/or higher plasma insulin levels.

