Fat formula: The formula used as the fat-test is prepared 24 hours in advance, and contains heavy whipping cream, ice cream, safflower oil, and a powdered protein source (Promod). The nutrient composition of the formula is 53 g fat/meter² and 300 mg cholesterol. The fat is approximately 50% saturated fat. LactaidTM is also added to each test formula preparation as a precaution against lactose-intolerance in any of the participants. On the day of the test the appropriate volume of formula, based on the patient's surface area (calculated from height and weight) is measured and served.

2. Day long postprandial sampling: The protocol is based on having the subjects come to the center for all three meals on a single day, with bloods obtained before breakfast (8-9 am), before lunch (12-1 pm) and before dinner (4-5 pm). As always, the fasting sample follows a 12 hour fast. Breakfast is completed within 30 minutes of the fasting sample and the pre-lunch sample is obtained 3.5 hours after the end of breakfast. Lunch is completed within 30 min of the pre-lunch sample and the pre-dinner sample is obtained 4.5 hours after the end of lunch.

Rationale: In addition to determining the chronic effects of dietary constituents to the metabolism of a standard fat load, it is useful to demonstrate the immediate effects of the diet on blood levels of certain variables. In this proposal we will measure plasma lipid, glucose and insulin levels before each meal at the end of each diet period. These studies will allow us to observe the actual day-long changes in these variables while participants eat diets differing in carbohydrate and fat content.

II. Methods of Analysis

A. Local Field Center Testing

Lipid Profiles, Glucose, Uric Acid

1. Columbia University.

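### In the day-long postprandial test, the 4.5-hour interval after lunch and the 4-5 pm window for the pre-dinner sample mostly do not overlap

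*Protocol*

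**What the plan says.** Chapter 9, section I.C (Post prandial studies), item 2 (Day long postprandial sampling) sets the three draws by the clock: "before breakfast (8-9 am), before lunch (12-1 pm) and before dinner (4-5 pm"). The opening paragraph of section I.C gives the same two later windows: "just before lunch (12-1 pm) and just before supper (4-5 pm").

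Item 2 then sets the same draws by elapsed time:
- Morning: "Breakfast is completed within 30 minutes of the fasting sample and the pre-lunch sample is obtained 3.5 hours after the end of breakfast".
- Afternoon: lunch has the same 30-minute limit, counted from the pre-lunch draw, and "the pre-dinner sample is obtained 4.5 hours after the end of lunch".

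On the analytes, section I.C says: "These samples would be analyzed for insulin, glucose and triglycerides". Chapter 9, Table 1 places this test in week 6, with draws before lunch and before dinner, and gives no clock time or interval. Chapter 3, section C, item 7 names postprandial measures as secondary endpoints that may be included. Table 1 lists them among the tests that allow sub-hypotheses to be tested.

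**The concern.** Two rules are given for one sample, and for most subjects they lead to different times. Four field centers must carry out the test, and nothing in the protocol says which rule wins when they disagree. Only two samples follow a meal on that day, so time since lunch is a large part of what the last one describes. If one center follows the clock and another the interval, the pooled pre-dinner triglyceride, glucose and insulin values are taken at different times after eating. If a subject's rule changed from one diet period to another, the timing difference would enter that subject's diet contrast.

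**Working it through.** **Inputs**, all from Chapter 9, section I.C: fasting draw 8:00-9:00 am; breakfast up to 0:30; 3:30 from the end of breakfast to the pre-lunch draw; lunch up to 0:30; 4:30 from the end of lunch to the pre-dinner draw; stated later windows 12-1 pm and 4-5 pm.

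**1. Pre-lunch window, 30-minute breakfast.** 8:00-9:00 + 0:30 + 3:30 = 12:00-1:00 pm. The stated window is reproduced exactly, so 30-minute meals are a fair reading of how the schedule was built.

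**2. Pre-dinner window, 30-minute lunch.** 12:00-1:00 + 0:30 + 4:30 = 5:00-6:00 pm. The stated window is 4-5 pm; the two touch only at 5:00 pm.

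**3. Interval that would fit the stated window.** Lunch ends at 12:30-1:30 pm, and 12:30-1:30 + 3:30 = 4:00-5:00 pm. Under the same convention the window matches 3.5 hours, one hour less than stated.

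**4. Shorter meals.** The protocol gives only a ceiling on meal length, so a distribution has to be assumed. Take the fasting draw T uniform over 8-9 am, and breakfast B and lunch L (in hours) independent and uniform over a range. Following the intervals:
- The pre-lunch draw is at or after noon when T + B is at least 8.5.
- The pre-dinner draw is at or before 5 pm when T + B + L is at most 9.
- Both hold for T between 8.5 − B and 9 − B − L, a stretch of length 0.5 − L that always lies inside 8-9 am. The share meeting everything is therefore 0.5 − mean(L).
- The share of pre-dinner draws after 5 pm, whatever the pre-lunch time, is mean(B) + mean(L).

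| Meal length (min) | Mean meal (h) | Pre-dinner draw after 5 pm | Both later windows and both intervals met |
|---|---|---|---|
| 0-30 | 0.250 | 50% | 25% |
| 10-30 | 0.333 | 67% | 17% |
| 15-30 | 0.375 | 75% | 13% |
| 20-30 | 0.417 | 83% | 8% |
| 30 | 0.500 | 100% | 0% (a single point, 8:00 am) |

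In the 0-30 minute case, 25% of pre-lunch draws fall before noon. Among the 75% that keep the pre-lunch window, 0.25 / 0.75 = 33% also have the last draw by 5 pm.

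**5. Clock windows alone, 30-minute lunch.** Shortest gap: pre-lunch draw 1:00, lunch ends 1:30, last draw 4:00, which is 2.5 hours. Longest gap: pre-lunch draw 12:00, lunch ends 12:30, last draw 5:00, which is 4.5 hours. A lunch of almost no length would extend the upper end to 5 hours.

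**The case against.** The case for leaving the text alone has several parts.

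- **Thirty minutes is a ceiling.** A reader might infer that no subject can meet both rules unless drawn close to 8 am. The text does not support that. A draw at 8:30, breakfast finished at 8:40, pre-lunch draw at 12:10, lunch finished at 12:20 and last draw at 4:50 pm meets every window and interval. This stands, and it is why the claim is that the rules mostly do not overlap.
- **A post-lunch time is stated.** A reader might infer that the last sample has no defined time after the meal. In fact the protocol names one, 4.5 hours. The trouble is that the window beside it usually points elsewhere.
- **Harm to the diet comparison is not shown.** A reader might argue that the analytes are still moving at 3.5 to 4.5 hours, or that triglyceride clearance is what this test is for. The protocol gives no figures for the first. For the second, chylomicron and remnant metabolism belongs to the separate standard fat load test, with samples at 4 and 8 hours. The day-long test is meant to observe levels before each meal.
- **The design absorbs much of it.** In a within-subject crossover, a center that keeps one rule in all three periods loses little, and nothing in the protocol suggests that a center would switch.
- **Manuals and forms are promised.** Chapter 9, sections III and V, refer to detailed manuals and to forms that document each collection step. Those are natural places for draw times, but meal-end time is not named, and a manual written from a contradictory text needs the contradiction settled first.

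These points limit the consequence. None removes the conflict between the two statements.

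**Conclusion.** The conflict is real and internal to section I.C. With 30-minute meals the stated interval and the stated window differ by one hour. With shorter meals only a minority of subjects, about 8% to 25% across the ranges tried, can meet both later windows and both intervals. The clock arithmetic needs only the protocol's figures; the percentages also rest on an assumed uniform spread of fasting draws and meal lengths and should be read as illustrations. Under the clock alone, time since a 30-minute lunch can run from 2.5 to 4.5 hours.

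The effect is confined to a secondary, optional measure. No primary endpoint, significance level or power figure is involved. The exposure lies in pooling across centers, in describing the sample correctly, and in the within-subject contrast only if the rule changes between periods. The documents do not show whether the interval or the window is the intended one.

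**What to change.** Reconcile the opening paragraph of section I.C with item 2 so that one rule, interval or clock window, governs the pre-dinner sample and the other is derived from it. With 30-minute meals, keeping the 4.5-hour interval gives a 5-6 pm window, and keeping 4-5 pm gives a nominal interval of 3.5 hours. The choice is the investigators'. State that the same rule applies at all four centers and in all three periods, and record the actual meal-end and draw times so that the achieved interval is known. Table 1 carries no clock time and needs no change.

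The cost is a wording correction in two places and a few time entries on a collection form. If the interval is kept, dinner on the test day of each period may fall about an hour later than the present window implies.

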APPENDIX A

List of Forms

۰.

۰.

APPENDIX A

	LIST OF DELTA FORMS
1.	Recruitment Log
2.	Telephone Screening Form
3.	Eligibility Visit 1 Screening Questionnaire
4.	Eligibility Visit 2 Screening Questionnaire
5.	Consent Form
6.	Participant Agreement
7.	Diet Compliance Forms
8.	Participant Weekly Tracking Form
9.	Close Out Form
10.	Drop Out Form
11.	Data Entry Form for Lipids and Lipoproteins
 	
12.	Data Entry Form for Hemostasis Variables
13.	Clinic Visit Form for Phlebotomy and BP
14.	Form to Use when Calibrating Weights for Scales
